1 PROTOCOL SYNOPSIS

Protocol Title	A Prospective, Randomized, Multicenter Study to Compare the Safety and Effectiveness of the OMNI® Surgical System and the iStent Inject in Pseudophakic Eyes with Open Angle Glaucoma- The TRIDENT European Trial
Study Device	OMNI Plus Surgical System (OMNI Surgical System)
Study Objectives	First, to compare safety and effectiveness outcomes for canaloplasty and trabeculotomy using the OMNI Surgical System to implantation of the iStent inject in lowering intraocular pressure (IOP) in pseudophakic eyes with open angle glaucoma (OAG), and second, to compare safety and effectiveness outcomes for canaloplasty alone (using the OMNI Surgical System) to implantation of the iStent Inject in lowering IOP in pseudophakic eyes with OAG.
Study Design	This is a prospective, randomized, multicenter, parallel group, comparative postmarket study in which a total of 459 subjects will be randomized in an equal allocation ratio (1:1:1) to either the OMNI (canaloplasty AND trabeculotomy), OMNI (canaloplasty only), or iStent inject and followed for 12 months after surgery.
Study Population	Pseudophakic adults with OAG.
Primary Effectiveness Endpoint	
Mean change in unmedicated DIOP from baseline at the 12-month postoperative examination 
The study hypotheses success will be evaluated using the primary effectiveness endpoint

OMNI System in Pseudophakic Eyes
Protocol 07062 Rev F

Other Effectiveness Endpoints	
• Proportion of eyes with a $\geq 20\%$ decrease in unmedicated mean diurnal IOP (DIOP) from baseline at the 12-month postoperative examination• Proportion of eyes with unmedicated mean DIOP between 6 and 18 mmHg inclusive at the 12-month postoperative examination• Mean change in the number of ocular hypotensive medications at the 12-month postoperative visit compared to Screening• Percent change in unmedicated DIOP from baseline to 12 months• Change in Ocular Surface Disease Index (OSDI) and Glaucoma Quality of Life (GQL-15) scores from screening at 12 months. 
These are the exploratory endpoints and will not be used to evaluate the study success.

Safety Endpoints	
• Rates of ocular adverse events (intraoperative, postoperative)• Reduction in best corrected distance visual acuity (BCDVA) from screening.• Secondary Ocular Surgical Interventions, including laser, for IOP control


Inclusion Criteria (Ocular criteria apply to the study eye only)
	
 1. Male or female subjects, 18 years or older 2. Pseudophakic. History of uncomplicated cataract surgery and posterior chamber IOL implantation without compromise to the lens capsule, zonular dehiscence/rupture or vitreous prolapse, [REDACTED] [REDACTED]. 3. Diagnosis of open angle glaucoma (OAG) including pigmentary and pseudoexfoliation substantiated using funduscopic exam (or OCT) and at least one reliable visual field test with the Humphrey automated perimeter using the SITA Standard 24-2 testing algorithm or an Octopus perimeter program G1 or G1X. Mean deviation score must be ≥ -12.0 dB (Humphrey) or ≤ 12.0 dB (Octopus). The visual field test may be historical (within 6 months prior to Screening Visit). If needed, visual field testing may be repeated between the Screening Visit and the Baseline Visit. 4. At the Screening visit, on 1-5 ocular hypotensive medications (fixed combinations counted as number of components) with a medicated IOP of ≤ 33 mmHg. 5. At the Baseline visit, unmedicated diurnal IOP of ≥ 22 mmHg (≥ 24 mmHg for at least one timepoint and no less than 21 mmHg at any time point) and ≤ 36 mmHg and ≥ 3 mmHg higher than the medicated IOP at the Screening visit. 6. Scheduled for ab-interno minimally invasive canal-based glaucoma surgery. 7. Shaffer grade of ≥ 3 in all four quadrants 8. Able and willing to comply with the protocol, including all follow-up visits. 9. Understands and signs the informed consent.

Exclusion Criteria
	
 1. Any of the following prior treatments for glaucoma: 
 o Suprachoroidal stent [REDACTED] [REDACTED]


(Ocular criteria apply to the study eye only unless otherwise stated)
	
 Implanted with a MIGS or other glaucoma device [REDACTED] Trabeculectomy or other bleb forming procedure [REDACTED] Prior canaloplasty, goniotomy, or trabeculotomy including procedures [REDACTED] Ciliary ablation procedures including Endocyclophotocoagulation (ECP), Cyclophotocoagulation (G probe), Micropulse laser, or high intensity focused ultrasound (HIFU) [REDACTED] 
2. Any other form of glaucoma other than OAG
 
3. Use of topical ocular steroids that cannot be stopped [REDACTED]
 
4. In the Investigator's judgement, predisposed to significant risk because of washout of ocular hypotensive medications.
 
5. Concurrent ocular pathology or systemic medical condition which, in the Investigator's judgment, would either place the subject at increased risk of complications, contraindicate surgery, place the subject at risk of significant vision loss during the study period (e.g., wet AMD, corneal edema, Fuch's dystrophy, active intraocular infection or inflammation within 30 days prior to Screening Visit, etc.), or interfere with compliance to elements of the study protocol (e.g., returning to investigator's office for follow-up visits).
 
6. History of penetrating keratoplasty or other corneal transplant; corneal abnormality that would prevent reliable IOP measurement (e.g. keratoconus, abnormally thick [$\geq 600 \mu\text{M}$] or thin [$\leq 500 \mu\text{M}$] cornea based on optical or ultrasound pachymetry of central corneal thickness [CCT])

--	---

	
7. BCDVA of 6/60 (20/200) or worse in the fellow eye not due to cataract
 
8. Participation of the study eye in any other ocular interventional study ≤ 30 days prior to Baseline visit and throughout this study
 
9. Women of childbearing potential if they are currently pregnant or intend to become pregnant during the study period; are breast-feeding; or are not in agreement to use adequate birth control methods to prevent pregnancy throughout the study.

Number of Subjects Enrolled and Treated	459 (153 per treatment group) to complete 411 (137 per group) at 12 months postoperative assuming a 10% drop-out rate
Number of Sites	A minimum of 24 and up to 26 sites in the European Union, United Kingdom, and/or Switzerland
Schedule of Visits	Screening, Baseline, Surgery (Day 0), Day 1, Week 1, 1 Month, 3 Month, 6 Month, 12 Month, 12 Month Washout
Treatments	
 • Ab-interno canaloplasty (360 degrees) and up to 360 degrees trabeculotomy using the OMNI Surgical System • Ab-interno canaloplasty (360 degrees) using the OMNI Surgical System • Ab-interno implantation of iStent inject (2 microstents)

2 STUDY OBJECTIVE

First, to compare safety and effectiveness outcomes for canaloplasty and trabeculotomy using the OMNI Surgical System to implantation of the iStent inject in lowering intraocular pressure (IOP) in pseudophakic eyes with open angle glaucoma (OAG), and second, to compare safety and effectiveness outcomes for canaloplasty alone (using the OMNI Surgical System) to implantation of the iStent Inject in lowering intraocular pressure (IOP) in pseudophakic eyes with open angle glaucoma (OAG).

Objective 1:

The first objective is to evaluate, if for pseudophakic eyes with OAG, OMNI (canaloplasty AND trabeculotomy), is superior in lowering IOP to iStent inject.

Mean change in **unmedicated** DIOP from baseline at the 12-month postoperative examination will be used as a primary effectiveness endpoint to evaluate superiority of OMNI (canaloplasty AND trabeculotomy) compared to iStent inject in lowering IOP in pseudophakic eyes with OAG.

Objective 2:

The second objective is to evaluate if canaloplasty alone is non-inferior in lowering IOP (with a non-inferiority margin of 1.5 mmHg for comparing mean unmedicated diurnal IOP reduction at 12 months postoperative) to the iStent inject.

Mean change in **unmedicated** DIOP from baseline at the 12-month postoperative examination will be used as a primary effectiveness endpoint to evaluate non-inferiority of OMNI canaloplasty compared to iStent inject in lowering IOP in pseudophakic eyes with OAG.

The hypothesis is that the combined canaloplasty + trabeculotomy will be superior to iStent Inject and canaloplasty alone will be non-inferior to iStent Inject in lowering the IOP. Unmedicated diurnal IOP will be used to measure the change in the IOP as the primary effectiveness endpoint. The statistical approach is described in detail in Section 10 of this protocol. Diurnal IOP takes into consideration the fluctuations in IOP throughout the day and medication washout allows for isolating the effect of study treatments (1. Canaloplasty + Trabeculotomy, 2. Canaloplasty alone and 3. Trabecular bypass shunt i.e. iStent inject).

3 BACKGROUND AND JUSTIFICATION FOR THE STUDY

Glaucoma is the leading cause of irreversible blindness worldwide and is a silent, progressive disease with global prevalence estimated at 76 million currently and 112 million by 2040.¹ The lack of symptoms (for OAG) and that significant loss of retinal ganglion cells can occur before glaucomatous visual field changes are detected underscore the need for consistent, effective treatment.^{2,3} Elevated IOP is the primary risk factor (and the only treatable) for glaucoma, and treatment for glaucoma is directed at lowering IOP either medically or surgically.⁴ The Ocular Hypertension Treatment Study showed that reduction of IOP by an average of 22.5% through medical intervention decreased conversion from ocular hypertension to glaucoma over a 5-year period to approximately half that of untreated controls (4.4 vs. 9.5%).⁵ Similarly, the EMGT showed that treatment of newly diagnosed primary OAG with argon laser trabeculoplasty plus betaxolol reduced the risk of disease progression at 6 years to half of that for untreated controls (hazard ratio, 0.50; 95% confidence interval, 0.35–0.71).⁶

Each mmHg of IOP reduction decreased the risk of progression by approximately 10%.⁶ AGIS showed that eyes with 100% of visits with IOP less than 18 mmHg over 6 years had mean changes from baseline in visual field defect score close to zero during follow-up.⁷ Preservation of vision in patients with glaucoma is clearly dependent on control of intraocular pressure. With medical therapy generally the first line of treatment, successful control of intraocular pressure is largely dependent on patient adherence.⁸⁻¹⁰ Unfortunately, nonadherence with medical glaucoma therapy is recognized to be a serious problem; Olthoff et al. concluded that nonadherence was commonplace.¹¹

Minimally (or micro) invasive glaucoma surgery (MIGS) provides an alternative to more invasive surgical methods (i.e. trabeculectomy or glaucoma drainage devices) or to laser procedures. MIGS procedures can generally be done along with cataract surgery minimizing additional risk or as standalone procedures. Several studies have demonstrated MIGS to provide long-term IOP lowering and the potential to reduce or eliminate the need for medications (and therefore reliance on patient adherence).^{12,13}

MIGS techniques that re-establish the aqueous outflow through the physiological pathways are gaining acceptance among glaucoma surgeons. Canaloplasty (originally described as ab externo) is one such procedure that is intended to restore the natural aqueous outflow system through microcatheterization and viscodilation of Schlemm's canal with a well-documented safety and efficacy profile in reducing IOP.¹⁴⁻¹⁶ Trabeculotomy is another such procedure that relieves the resistance to aqueous flow by cleaving the trabecular meshwork and the inner wall of Schlemm's canal, resulting in pressure reductions.^{17,18}

The OMNI Surgical System (Sight Sciences Inc, Menlo Park, CA) is a manually operated device indicated for the delivery of small amounts of viscoelastic fluid and to cut trabecular meshwork tissue during trabeculotomy procedures. The OMNI allows doctors to perform viscoelastic delivery in conjunction with trabeculotomy through a single clear corneal incision. Alternatively, the OMNI may be used to perform canaloplasty only (without trabeculotomy). The OMNI Surgical System may be used in a combined procedure with phacoemulsification cataract surgery, or as a standalone procedure in pseudophakic patients.

The iStent inject (Glaukos Corp., San Clemente, CA) is intended to reduce intraocular pressure safely and effectively in patients diagnosed with primary open-angle glaucoma, pseudoexfoliative glaucoma or pigmentary glaucoma. The iStent inject can deliver two (2) stents on a single pass, through a single incision. The implant is designed to stent open a passage through the trabecular meshwork to allow for an increase in the facility of outflow and a subsequent reduction in intraocular pressure.

The device is safe and effective when implanted in combination with cataract surgery in those subjects who require intraocular pressure reduction and/or would benefit from glaucoma medication reduction. The device may also be implanted in patients who continue to have elevated intraocular pressure despite prior treatment with glaucoma

medications and conventional glaucoma surgery. The CE mark for this device was obtained in 2011.

This prospective, multicenter, randomized, comparative trial will evaluate and compare clinical outcomes for ab-interno canaloplasty and trabeculotomy performed using the OMNI Surgical System, for canaloplasty only using the OMNI Surgical System, and for the iStent inject, all used as standalone procedures (i.e., not in combination with cataract surgery) in patients with OAG.

Note: A summary of known and potential risks to humans, as identified in the literature or through preclinical testing and/or prior clinical evaluations for the study devices can be found in the Instructions for Use for the OMNI Surgical System or the iStent inject.

4 STUDY DEVICE

4.1 INDICATIONS FOR USE

The OMNI Plus Surgical System is CE marked and has the following indication for use:

[figure not shown]
Catheterization and transluminal viscodilation of Schlemm's canal and the cutting of trabecular meshwork to reduce intraocular pressure in adult patients with open-angle glaucoma.

4.2 DEVICE DESCRIPTION

The OMNI Plus Surgical System "OMNI" is a single-handed, manually operated device designed to provide metered delivery of viscoelastic gel into Schlemm's canal and to cut trabecular meshwork tissue using a microcatheter. The device integrates an access cannula, a microcatheter, an internal fluid reservoir, and a simple catheter advancement and retraction wheel mechanism all into a single disposable handheld device.

Using only a single clear corneal incision to access the trabeculocanalicular aqueous outflow system, the OMNI Glaucoma Treatment System facilitates the transluminal viscodilation of all 360 degrees of Schlemm's canal and the cutting of up to all 360 degrees of trabecular meshwork from an ab interno approach. The system can be used with commercially available viscoelastics, such as Healon® PRO or Healon GV® PRO from Johnson & Johnson Vision, Amvisc® from Bausch & Lomb, or PROVISC® from Alcon. Viscoelastic fluid is not provided with the device.

5 STUDY DESIGN

This is a prospective, randomized, multicenter, parallel group, comparative study in which a total of 459 subjects will be randomized in an equal allocation ratio (1:1:1) to either the OMNI (canaloplasty AND trabeculotomy), OMNI (canaloplasty only), or iStent inject and followed for 12 months after surgery.

The study will employ a medication washout pre-randomization and at the 12-month endpoint which eliminates the potential confounding influence of ocular hypotensive medications in the assessment of device effectiveness.

5.1 NUMBER OF SUBJECTS, DURATION OF FOLLOW-UP AND STUDY DURATION

Approximately 459 subjects will be randomized (1:1:1) to treatment, approximately 153 in each group. This assumes a 10% drop-out rate over the 12-month follow-up period and ensures that 137 subjects per group will complete the 12 month study. No site will randomize more than 25% of the total number of subjects.

It is estimated that up to 40% of subjects will not meet IOP eligibility criteria following medication washout, or other inclusion/exclusion criteria failure preventing

randomization therefore up to 762 subjects may be enrolled in order to meet the targeted randomization of 459 subjects.

Study subject participation will be for approximately 12 months, 5 days (at a minimum) to 14 months, depending on the length of the required medication washout prior to baseline and if a terminal washout is needed (required for subjects presenting at the Month 12 visit and on ocular hypotensive medication).

It is anticipated that site initiation, subject recruitment and follow-up, and site close-out will require approximately 24 months.

5.2 METHODS USED TO MINIMIZE BIAS

This study is randomized using block (a block of 6) randomization and neither the Investigator, the investigative site staff, or Sponsor clinical personnel will have knowledge of or access to the randomization scheme. Randomization to treatment group will be performed using a 1:1:1 ratio and will be stratified by site. Treatment allocation bias will thus be avoided. Once randomized into the study, the Investigator, the investigative site staff, Sponsor clinical personnel and the subject will be unmasked to the treatment assignment for each subject.

The study is multicenter with sites in at least 5 countries. The potential bias inherent in single-center trials is thus eliminated. Moreover, no site can randomize more than 25% of the study subjects. The location of sites in multiple countries incorporates greater diversity in the patient population as well as subtle geographic differences in treatment norms/standard of care allowing greater generalizability of the study results.

Mean diurnal IOP is the basis for the primary endpoint. DIOP averages three separate IOP measurements taken at different times of day. This mitigates the risk of a single measurement being unusually high or low and subsequent regression to the mean. IOP measurements will be taken using Goldmann applanation tonometry with routine and documented calibration required. IOP will be measured by 2 different study personnel (an operator and a recorder) closely following the procedure used in AGIS.¹⁹ This technique prevents unintentional bias on the part of the Investigator or technician measuring and recording the IOP.

Reintroduction and discontinuation of ocular hypotensive medications will follow a protocol defined procedure to ensure standardization across sites and remove the potential for bias in treatment regimen.

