7 STUDY SELECTION CRITERIA

7.1 INCLUSION CRITERIA

For inclusion in this study, subjects must meet all the following criteria (only one eye of each subject is eligible, and all ocular criteria apply to the study eye only unless otherwise indicated):

1. Male or female subjects, 18 years or older
2. Pseudophakic. History of uncomplicated cataract surgery and posterior chamber IOL implantation without compromise to the lens capsule, zonular dehiscence/rupture or vitreous prolapse, [REDACTED].
3. Diagnosis of open angle glaucoma (POAG) including pigmentary and pseudoexfoliation substantiated using funduscopic exam (or OCT) and at least one reliable visual field test with the Humphrey automated perimeter using the SITA Standard 24-2 testing algorithm or an Octopus perimeter program G1 or G1X. Mean deviation score must be ≥ -12.0 dB (Humphrey) or ≤ 12.0 dB (Octopus). The visual field test may be historical (within 6 months prior to Screening Visit). If needed, visual field testing may be repeated between the Screening Visit and the Baseline Visit.
4. At the Screening visit, on 1-5 ocular hypotensive medications (fixed combinations counted as number of components) with a medicated IOP of ≤ 33 mmHg.
5. At the Baseline visit, unmedicated DIOP of ≥ 22 mmHg (≥ 24 mmHg for at least one timepoint and no less than 21 mmHg at any time point) and ≤ 36 mmHg and ≥ 3 mmHg higher than the medicated IOP at the Screening visit.
6. Scheduled for ab-interno minimally invasive canal-based glaucoma surgery.
7. Shaffer grade of ≥ 3 in all four quadrants
8. Able and willing to comply with the protocol, including all follow-up visits.
9. Understands and signs the informed consent.

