8 STUDY PROCEDURES

8.1 PROCEDURES PER STUDY VISIT

[figure not shown]
Procedures required by the protocol to be conducted at each study visit are listed in the Table 1, Study Visit Schedule and detailed in Appendix A, Section 19.1 CLINICAL TRIAL PROCEDURES.

A brief summary of the procedures performed by visit is provided here.

- At Screening, the subject will complete the informed consent process and sign an informed consent document. Standard procedures will be performed to determine subject eligibility. If needed, a second visual field exam may be conducted before surgery to confirm study eligibility. Wash-out of ocular hypotensive medications will commence.
- At Baseline, eligibility will be confirmed including meeting the unmedicated DIOP criteria. Eligible subjects will be randomized to treatment and scheduled for surgery. Ineligible subjects will be exited.
- At Surgery, subjects will either receive canaloplasty and trabeculotomy in the study eye with the OMNI Surgical System, canaloplasty with the OMNI Surgical System or be implanted with the iStent inject.
- At postoperative follow-up (Week 1, Months 1, 3, 6, and 12), safety and effectiveness assessments will be performed.

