8.4 STUDY VISITS

8.4.1 SCREENING VISIT

Informed Consent and Point of Enrollment

Informed consent will be obtained in writing from all subjects and the process documented prior to the performance of any procedure specific to the study using the Ethics Committee approved informed consent form. The Investigator or a trained authorized designee will conduct the informed consent process. Subjects will be given ample time to read and understand the informed consent form and to consider participation in the study. Subjects will be given a copy of the signed and dated informed consent form.

After obtaining an understanding of the purpose of this study, then providing written informed consent, all potential subjects will undergo an initial screening examination in order to determine their eligibility for the study. Exams and tests listed in the Screening column of Table 1 should be performed. Refer to Appendix A for instructions for performing the exams.

The Investigator must retain the original, signed written informed consent document.

Eligibility and Study Entry

Below is a list of study procedures to be undertaken at Screening Visit which must take place from 45 days to 6 days before surgery. Data collected at screening are considered baseline data. Conduct ocular assessments in both eyes.

1.	[REDACTED]
	[REDACTED]
	[REDACTED]
	[REDACTED]

Following confirmation of eligibility per study inclusion and exclusion criteria, subjects will be scheduled for the Baseline visit allowing sufficient time for complete washout of ocular hypotensive medication (refer to Table 2). Ineligible subjects must be exited from the study. The reason for ineligibility must be documented for each enrolled subject.

Subjects who are currently taking IOP-lowering medications will undergo the washout procedure described below and in Table 2 before the Baseline visit.

Subject exam data collected prior to enrollment as part of routine patient care may serve as Screening data as long as it was collected within 15 days prior to the visit with the following exceptions:

- IOP and IOP-lowering medications. These data must be collected at the Screening visit.
- Visual fields: A historical visual field may be used IF conducted per the protocol method (Humphrey automated perimeter using the SITA Standard 24-2 testing algorithm or an Octopus perimeter program G1 or G1X.) AND is within 6 months of the Screening visit.

Washout of Hypotensive Medications

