Below is a list of study procedures to be undertaken at the Baseline Visit which must take place no more than 14 days prior to surgery and only after satisfying the medication washout (Section 8.4.1. "Washout of Hypotensive Medications" and Table 2). Conduct ocular assessments in both eyes.

[figure not shown]
Subjects meeting all criteria at the Baseline Visit will be scheduled for surgery and be randomized to a treatment arm. Randomization to treatment group will be performed using a 1:1:1 ratio and will be stratified by site. Computer-generated randomization will be administered through the electronic data capture (EDC) system with separate block randomization (block of 6) sequences for each clinical site.

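### A fixed block of 6 per site, printed in the protocol of an unmasked trial, makes on average 20% of assignments in complete blocks foreseeable, so section 5.2 claims too much when it says allocation bias is avoided

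*Combined protocol and SAP*

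**What the plan says.** Section 5.2 of the combined protocol and SAP describes the method: "This study is randomized using block (a block of 6) randomization and neither the Investigator, the investigative site staff" or sponsor clinical personnel is to have access to the scheme. Allocation is 1:1:1 and stratified by site. The section then concludes "Treatment allocation bias will thus be avoided". The next sentence reads "Once randomized into the study, the Investigator, the investigative site staff, Sponsor clinical personnel and the subject will be unmasked to the treatment assignment".

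Section 8.4.2 (Baseline Visit) adds that the EDC system runs "separate block randomization (block of 6) sequences for each clinical site". Under section 16.3 the principal investigator at each centre agrees to and signs this protocol.

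On entry, section 8.4.1 says "Following confirmation of eligibility per study inclusion and exclusion criteria, subjects will be scheduled for the Baseline visit", and section 8.1 says "At Baseline, eligibility will be confirmed including meeting the unmedicated DIOP criteria". Randomisation follows. Section 8.4.1 also requires "The reason for ineligibility must be documented for each enrolled subject".

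**The concern.** The EDC system hides the list, but prediction does not need the list. It needs the ratio, the block size, the stratum and the past assignments. The protocol prints the first three, and an unmasked site sees the fourth. The sentence that denies knowledge of the scheme itself gives the block size, and the visible text describes no step against prediction.

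Foreknowledge matters where a site can still influence who takes the next slot. Routes before randomisation include:

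- exclusion 5, which rests on the Investigator's judgement (exclusion 4 is a weak route at Baseline, because it concerns the risk of washout and the preoperative washout is then complete);
- the choice of whom to consent and when;
- the Investigator's discretion under section 8.8 to discontinue a subject;
- some slack in the timing of the Baseline visit.

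Section 5.1 expects up to 40% of subjects to fail before randomisation, so one more exclusion would not stand out. Selection by arm in an open-label surgical trial cannot be fully removed by later analysis, and section 5.2 relies on this scheme as the protection against it.

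**Working it through.** The plan gives no predictability figure to reproduce. As a check on the design inputs, 137 / 0.9 = 152.2, rounded up to 153 per group, and 3 × 153 = 459, as in section 5.1.

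**One block.** Each block of 6 holds two of each arm, so there are 6!/(2!·2!·2!) = 90 equally likely orders. An assignment is certain when all the slots left belong to one arm.

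- Positions 1 to 4: probability 0.
- Position 5: the last two slots hold the same arm in 3 × 4!/(2!·2!) = 18 of the 90 orders, so 18/90 = 0.2.
- Position 6: probability 1.

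The sum is 1.2 per block, and 1.2/6 = 20%. This is an average, not a ceiling: a block gives 1/6 = 16.7% with probability 0.8, or 2/6 = 33.3% with probability 0.2. The best guess is right with probability 0.333, 0.40, 0.50, 0.533, 0.60 and 1.0 by position, a mean of 56.1% against 33.3% by chance.

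**Whole trial.** Incomplete last blocks lower the share. Expected certain assignments per site are 0.2 for 5 subjects, 2.4 + 0.2 = 2.6 for 17, and 3 × 1.2 = 3.6 for 18, 19 or 20. Site sizes are an assumption, because the plan states only a 25% cap per site. The number of sites is itself inconsistent: the synopsis says 24 to 26, section 5.4 says up to 24.

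| Assumed spread of 459 subjects | 24 sites | 26 sites |
|---|---|---|
| Even | 24 × 3.6 = 86.4 (18.8%) | 17 × 3.6 + 9 × 2.6 = 84.6 (18.4%) |
| Random, equal chance per site (simulated) | 80.6 (17.6%) | 79.7 (17.4%) |
| Half the sites at 5, the rest even | 12 × 0.2 + 12 × 6.0 = 74.4 (16.2%) | 13 × 0.2 + 13 × 6.0 = 80.6 (17.6%) |

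**Timing slack.** Section 8.4.3 allows 45 days from Screening to surgery. With a longest washout in Table 2 of 28, 14 or 5 days, the slack is at most 45 − 28 = 17, 45 − 14 = 31 or 45 − 5 = 40 days, less any gap between Baseline and surgery.

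**Varying block sizes.** Simulated sites of 19 subjects, sizes equally likely, for an observer who knows the set of sizes but not their order:

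| Block sizes | Certain | At least one arm ruled out | Best guess right |
|---|---|---|---|
| 6 | 18.9% | 44% | 55% |
| {3,6} | 7.5% | 20% | 56% |
| {6,9} | 4.7% | 13% | 52% |
| {6,9,12} | 1.9% | 6% | 51% |

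**Arm imbalance.** Under the random spread, the mean gap between the largest and smallest arm rises from about 5 to between 6 and 7 subjects, with a 95th percentile of up to about 14. At a gap of 14, comparing arms of 146 and 160 gives a standard error of √[(1/146 + 1/160)/(2/153)] = 1.001 times that of equal arms, or 0.1% wider. If the two arms compared are both the small ones (148 and 149 against 162), the ratio is √[(1/148 + 1/149)/(2/153)] = 1.015.

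**The case against.** The strongest reply is that the plan limits what a site could do with this knowledge, and much of that stands. The list is held centrally. The Baseline pressure criteria are numeric, for example "no less than 21 mmHg at any time point". Eligibility is first confirmed at Screening, before washout, and reasons for ineligibility are documented. Section 8.8 also obliges the Investigator to try to keep subjects in the study, and requires the reason for any early withdrawal to be recorded. These measures deter selection but do not prevent it. Parts of the visit procedures are not visible, so further safeguards or further routes may exist, and the routes listed above are not a complete count.

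A second reply is that the gain from varying blocks is modest. That also stands in part: best-guess accuracy falls by only three or four percentage points. The gain lies in certain and ruled-out assignments.

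A reader might infer that allocation has been biased, or that the type I error of either hypothesis is inflated. The documents support neither. They show that assignments can be deduced, not that any site counts them or acts on them.

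**Conclusion.** The point holds as a limit on what section 5.2 can claim. With a disclosed fixed block of 6 per site and unmasked staff, 20% of assignments in complete blocks are foreseeable on average to a site that counts. Over the trial that is about 74 to 86 of 459 subjects (16% to 19%) under the site sizes assumed above. The 20% is exact for complete blocks; the trial-wide range depends on site sizes that the plan does not state. The described method reduces the risk of allocation bias but does not exclude it. The wording should change in any case. The case for changing the blocks depends on how many subjects remain to be randomised, which the documents do not say.

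**What to change.** 1. In any case, reword the sentence in section 5.2 to say that the risk of treatment allocation bias is reduced.
2. If a material number of subjects remain to be randomised, use randomly varying block sizes, such as {6,9} or {6,9,12}, for blocks not yet started at each site. Avoid {3,6}, which leaves more certain assignments and no lower best-guess accuracy. Move the block sizes from sections 5.2 and 8.4.2 to a restricted randomisation specification.

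If randomisation is complete or nearly so, do the first only.

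The rewording is a text change with sponsor approval and, as necessary, ethics review under section 13. The second change also needs a new list in the EDC system and accepts slightly more arm imbalance, with the small loss of precision shown above. It cannot repair what is done: sites that hold the current text know the block size used so far.
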